The number of days required for clinical improvement

1. Early Clinical improvement of the patients
How many days it requires to become the patient completely symptoms free
[Time Frame: 7 days]
2. Late clinical recovery
How many days the symptoms persist
[Time Frame: 12 days]

Secondary Outcome Measure:

1. Percentage of patients having clinical deterioration.
Patients deteriorating to next level of severity, like moderate, severe and death
[Time Frame: 1 month]
2. Persistently positive for RT-PCR.
Percentage of Covid-19 Patients repeatedly become positive for RT-PCR for Covid-19
[Time Frame: 14 days]

Data collection technique:

Data will be collected by assigned. trained data collectors (Physician).

Patient will be enrolled according to defined inclusion and exclusion criteria in the current research. Informed written consent will be obtained from the patient or their relatives. Each patient participating in the trial will be uniquely identified, and information such as his name, address is recorded in the trial 'subject number list'. Only the principle investigator will be aware about the allocation of the drugs. The patients

and the data collectors will be unaware about the group allocation of the drugs. The Data will be reviewed by the co-investigators. It will be managed by principle and co-principle investigators in designated computer.

Clinical assessment (fever, cough, Anorexia, Temperature, pulse, blood pressure, respiratory rate, oxygen saturation) will be done every day. Routine investigation (CBC, ESR, CRP, Creatinine, RBS, SGPT, chest x-ray, D- Dimer) will be done at admission and at day 3, 5, 7, 10 and 14 day. In case of the clinical deterioration it would done according to necessity. RT-PCR will be done at day-0, Day 5, day 7 and day 14.

Standard care: both the experimental and placebo will receive the available standard of care, like-

- Paracetamol, Antihistamine, Cough suppressant, Vitamins
- Oxygen therapy according to indication and need
- Low molecular weight heparin according to indication
- Appropriate other broad spectrum antibiotics
- Other drugs for associated co- morbid condition

Management of the adverse events:

Drugs adverse effect will be monitored by a defined committee. The patient experiencing adverse effect of the drugs will be discontinued from the study. It will be managed with priority to the highest possible level by the hospital authority as well as the investigators.

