If the patient progresses from mild to moderate or severe disease, the study will be continued and available management of the appropriate severity will be immediately started. The patient will be monitored closely.

Data analysis:

Data will be analyzed by computer with the help of SPSS (Statistical Package for Social Sciences) version 20. To compare mean of the two group chi square will be used. Comparing drug outcome in between two group survival analysis by Kaplan-Meier curve will be done for the duration of recovery. Odds ratio will be formulated from linear logistic regression for early and late clinical recovery. Hazard ratio will be formulated from the cox regression analysis for severity conversion and persistence of the positivity. Crude odds ratio will be adjusted in cox proportional hazard ratio model. Each Ivermectin-Doxycycline plus standard of care group will be compared with the placebo plus standard care group using the log-rank test, hazard ratio and 95% CI. Participants who were lost to follow up, died, discontinue drugs due to adverse effect will censored on the last study day. All P values will be two-sided and will be shown without

adjustment for multiple testing. All analyses will be performed according to the intention to treat principle.

Dropout management: Intention to treat measure will be taken

Observation and Results:

Result of the study and statistical analysis will be presented by tables, figures, graphs, diagrams, charts and photographs. All these would have own legends (i.e. title) and will be serially numbered.

Discussion:

Discussion will be done on the basis of result obtained from the study and comparing with similar studies done at home and abroad.

Summary:

Summarization will be drawn after discussion.

Conclusion:

Conclusion would be drawn depending upon the results and discussion

Conflict of interest:

Popular pharmaceutical will only provide drugs and the placebo.
None of the investigators will receive remuneration from the pharmaceutical company.
They will not get any access to data profile.

Operational definition:

(According to WHO guideline)

Confirmed Covid-19:

Cases with positive RT-PCR for Covid 19 irrespective of symptoms.

Uncomplicated (mild) Illness

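### Deaths and adverse-effect withdrawals are censored, although death is a deterioration outcome and every analysis is declared intention to treat

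*Protocol*

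**What the plan says.** All places are in section 4 (Methodology) of the protocol.

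- **Data analysis, censoring:** "Participants who were lost to follow up, died, discontinue drugs due to adverse effect will censored on the last study day". No endpoint is exempted, and the last study day is not defined.
- **Data analysis, principle:** "All analyses will be performed according to the intention to treat principle". The separate line on dropouts adds only "Dropout management: Intention to treat measure will be taken".
- **Management of the adverse events:** "The patient experiencing adverse effect of the drugs will be discontinued from the study". The protocol then says that a patient whose disease progresses continues in the study.
- **Primary Outcome Measure:** "The number of days required for clinical improvement", with time frames of 7 days (early) and 12 days (late). The Data analysis section states that "survival analysis by Kaplan-Meier curve will be done for the duration of recovery", and adds a log-rank test and hazard ratio.
- **Secondary Outcome Measure 1:** a percentage of patients with clinical deterioration over 1 month, explained as "Patients deteriorating to next level of severity, like moderate, severe and death". Its model-based analysis is given under Data analysis: "Hazard ratio will be formulated from the cox regression analysis for severity conversion and persistence of the positivity".

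**The concern.** Two pairs of stated rules do not fit together.

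First, an intention-to-treat analysis needs the outcome of every randomised patient, whatever happens to treatment. The protocol ends participation for patients with an adverse effect and censors them. They stay in the denominator in name, but what happens to them afterwards is not used and may not be collected.

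Second, death is an outcome in one place and a reason for censoring in another. The percentage that deteriorate and the hazard ratio for deterioration would then count different events under one name.

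Censoring is harmless only if patients who are censored have the same later prospects as those who remain. That cannot be true of the dead, and it is doubtful for patients who leave because of an adverse effect. Outcomes that are never collected cannot be restored at analysis, so the point has to be settled before enrolment.

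**Working it through.** The protocol gives no figure for this point: no death rate, adverse-effect rate or deterioration rate. The check is a comparison of the rules, followed by illustrations on assumed values that test whether a direction can be claimed.

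**1. What each reading of the last study day does**

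| Patient | Own last day | End of window |
|---|---|---|
| Death, recovery analysis | Assumed to recover later like survivors: informative | At risk to the end, not recovered: acceptable |
| Adverse-effect exit, recovery analysis | Assumed to recover later like those remaining: informative | Counted as known unrecovered, though not observed |
| Lost to follow-up, recovery analysis | Ordinary censoring | Counted as known unrecovered, though not observed |
| Death without an earlier recorded step, deterioration | Censored: non-event | Censored: non-event, free of deterioration for the whole month |

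The last row is wrong under both readings. Such deaths are possible in the data as designed: the daily clinical record in the Case Record Form stops at day 14, while the outcome runs for 1 month.

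**2. Recovery: does the bias have a fixed direction?**

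Assumptions: recovery is exponential with 40% recovered by day 7 (the protocol's standard-treatment response rate, used here as a day-7 figure). In the active arm, 10% have an adverse effect, have not recovered by day 3 and leave at day 3. The 10% and the day are mine.

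- Day-12 recovery without the problem: 1 − 0.6^(12/7) = 58.3%.
- Kaplan-Meier, exits censored at day 3: 1 − (0.10 + 0.90 × 0.6^(3/7)) × 0.6^(9/7) = 1 − 0.8230 × 0.5185 = 57.3%.
- Exits held as unrecovered to day 12: 0.90 × 58.3% = 52.5%.

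The truth depends on what the withdrawn 10% would have shown:

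| Withdrawn patients by day 12 | True | Own-day reading | End-of-window reading |
|---|---|---|---|
| None recovered | 52.5% | 57.3% (4.8 points too high) | 52.5% (no bias) |
| Recovered like the others | 58.3% | 57.3% (1.0 point too low) | 52.5% (5.8 points too low) |

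The estimate is the same down each column while the truth moves by 5.8 points. The sign on the own-day reading turns on information that the plan does not collect.

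**3. Deaths in the recovery analysis**

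Assume 58% recover by day 7 among survivors, spread evenly over the days, with 3% dying after day 4. The true proportion is 0.97 × 58% = 56.3%. Kaplan-Meier gives 57.4% on the own-day reading and 56.3% on the end-of-window reading.

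**4. Deterioration**

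Assume true risks of 10% (active) and 18% (placebo), a ratio of 10/18 = 0.56. Crude risk ratios stand in for the hazard ratio. If deaths with no earlier step are not counted:

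- 0% active and 3% placebo: 10/15 = 0.67.
- 2% active and 0% placebo: 8/18 = 0.44.

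The ratio can move either way.

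**The case against.** Several stronger readings are tempting, and the documents do not support them.

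- **That either reading spoils the handling of deaths in the recovery analysis.** It does not. Holding a death at risk to the end of the window is a sound way to count it as not recovered, as step 3 shows.
- **That the rule favours the active arm.** A reader might infer this because diarrhoea and vomiting are symptom rows in the Case Record Form and might also be drug effects. The protocol does not say that they are, and it gives no rate or duration. Step 2 shows the direction reversing on plausible alternatives and vanishing in one.
- **That power falls from 95% to 84%.** This comes from taking 20% as lost and unrecovered: 0.80 × 58% = 46.4% against 0.80 × 40% = 32.0% at 200 per group. The protocol's 20% also covers refusals, and the calculation assumes that every loss comes before any recovery. The 95% it is compared with assumes no loss at all; if 20% simply contributed nothing, 160 per group would give 89.9%. It is no measure of this problem.

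Two further objections narrow the point. The Data analysis section speaks of stopping drugs, so the adverse-event section may mean stopping treatment loosely rather than leaving the study. That is possible, but the censoring sentence lists stopping drug as a reason in itself, so a later observed recovery would still not count. Also, the stated percentage that deteriorate is not affected by the censoring sentence. Only the hazard ratio of a secondary outcome is exposed, only for deaths without an earlier recorded step, and in mild and moderate patients these may be few. Both limits stand, and neither removes the contradictions.

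**Conclusion.** The plan is wrong as written on two counts. Removing and censoring patients with adverse effects contradicts the intention-to-treat statement. Censoring deaths contradicts the definition of deterioration, and this second fault does not depend on how the last study day is read. In the recovery analysis the undefined last study day leaves a choice between informative censoring of deaths and adverse-effect exits, and treating lost and withdrawn patients as known unrecovered.

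No direction or magnitude is claimed. The figures above rest on assumed rates and timings and show only that the result can shift by several points, or a risk ratio by about 0.1, in either direction. If deaths and adverse-effect exits prove rare, the effect will be small. It should still be corrected beforehand, because the missing outcomes could not be recovered later.

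**What to change.** Replace the censoring sentence and reconcile it with the adverse-event section:

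1. Patients who stop study drug for any reason remain in outcome follow-up and contribute their observed outcomes. Amend the adverse-event section to match the intention-to-treat statement. Whether drug is stopped is a clinical matter and is not addressed here.
2. Death is an event in the deterioration hazard ratio, as it already is in the percentage outcome.
3. In time to recovery, a patient who dies is kept as not recovered to the end of the stated window (day 7 or day 12).
4. Only patients truly lost to follow-up are censored, at their last actual assessment. Delete the reference to the last study day, or define it.

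The cost is a few sentences of wording and continued assessment of the patients who stop drug. The Case Record Form schedule already runs to day 14, which covers both recovery windows. The 1-month deterioration outcome lies beyond it and needs a status check for these patients, as it does for all others.

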Covid-19 is an emergent pandemic, threatens the life of millions of the people throughout the globe. There is increasing effort of the scientist to unveil a remedy of covid-19. Still it is unsuccessful. At present there is no other alternative other than experimenting the existent drug against the virus. There are several trials going throughout the globe. Among them Ivermectin showed good efficacy in vitro trial. Some clinical trial also proved it beneficial. The Doxycycline also has some anti-viral role with its prominent anti-inflammatory role. Synergistic action of the two drugs might be proved some benefit in clinical trial. As both drugs are cheap and less toxic, if it does, it would be the blessing for the poor people of the globe.

4. METHODOLOGY:

Study type: Interventional Clinical trial

Estimated enrollment: 200 participants per group

For superior trial, the formula is:

$$N = \frac{1}{2} \times \left(\frac{Z_{\frac{\alpha}{2}} + Z_{\beta}}{\arcsin \sqrt{p} - \arcsin \sqrt{P_0}} \right)^2$$

N=size per group; p=the response rate of standard treatment group; p₀= the response rate of new drug treatment group; z_x= the standard normal deviate for a one or two sided x; d=

the real difference between two treatment effect; δ_0 = a clinically acceptable margin; S^2 = Pooled standard deviation of both comparison groups.

All parameters were assumed as follows: $p = 0.40$; $p_0 = 0.58$; $\alpha = 0.05$; $\beta = 0.20$; $\delta = 0.18$; $\delta_0 = 0.10$.

$$N_{\text{statistical superiority}} = \frac{1}{2} \times \left(\frac{1.96 + 0.845}{\arcsin \sqrt{0.40} - \arcsin \sqrt{0.58}} \right)^2 = 121$$

However, we are assuming that lost to follow up or refuse to include in trial will be 20%, that means 24. So at least 150 patients will be allocated randomly and power of this study will be 80%.

Allocation:

Randomized: Block randomization (Computer generated randomization code)

Intervention model: Parallel assignment

Intervention model description: Patient will be randomized 1:1 to placebo with standard care and combined doxycycline and ivermectin with standard care.

Blinding: Double blind (The participant and the clinicians/data collectors will be unaware of the treatment the participant receives)

Primary purpose: Treatment

Official title: A phase III trial to promote recovery from covid 19 with combined Doxycycline and Ivermectin along standard care.

Provider of placebo and active ingredients: Popular pharmaceutical limited

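### Two listed primary measures and a survival analysis of recovery, all with unadjusted P values and no deciding test: type I error would be about 7–12% rather than 5% if any one success could carry the claim

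*Protocol*

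**What the plan says.** - **Opening summary (before Part D).** One primary outcome: days from randomisation to clinical improvement.
- **Primary Outcome Measure.** The lead line is again a single quantity, "The number of days required for clinical improvement". Two numbered measures follow: "Early Clinical improvement of the patients" with a 7-day time frame, and "Late clinical recovery" with a 12-day time frame. Both are worded as a number of days.
- **Data analysis, the two measures.** "Odds ratio will be formulated from linear logistic regression for early and late clinical recovery".
- **Data analysis, recovery time.** "survival analysis by Kaplan-Meier curve will be done for the duration of recovery". A later sentence compares the arms by log-rank test with hazard ratio and 95% CI, without naming the endpoint.
- **Data analysis, multiplicity.** "All P values will be two-sided and will be shown without", continuing "adjustment for multiple testing. All analyses will be performed according to the intention to treat principle". The sentence covers all P values and does not set the primary ones apart.
- **4. Methodology, Estimated enrollment.** One binary comparison, 0.40 versus 0.58, alpha 0.05, beta 0.20, giving 121 per group. The response rate is not tied to day 7, day 12 or time to recovery. The text gives 200 per group in one place and at least 150 patients in another, with 20% loss assumed.

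**The concern.** The protocol labels itself a phase III superiority trial, and its sample size treats the efficacy claim as one test at 5%. The analysis text offers up to three overlapping looks at the same recovery data and does not say which one decides or how they combine. The success rule is therefore open, and it could be settled after the results are known.

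This goes beyond detail left to a statistical analysis plan. The protocol states a rule, no adjustment for any P value, and applies it to measures it lists as primary. An analysis plan that controlled the error by adjusting those P values would contradict the protocol.

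**Working it through.** **1. The plan's own sample size.** Formula: N = ½ × [(1.96 + 0.845) / (arcsin√0.40 − arcsin√0.58)]².
- arcsin√0.40 = 0.6847 and arcsin√0.58 = 0.8657, so the difference is 0.1810.
- 2.805 / 0.1810 = 15.495, and ½ × 15.495² = 120.05, rounded up to 121. This reproduces the stated figure and is for one comparison at two-sided 0.05.

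**2. Error if either measure could carry the claim.** Assume each is tested at 0.05.
- If independent: 1 − 0.95² = 9.75%.
- They are not independent, because everyone recovered by day 7 is also recovered by day 12. With p7 = proportion recovered by day 7 and q12 = proportion not recovered by day 12, the correlation of the two test statistics is ρ = √[p7·q12 / ((1 − p7)(1 − q12))]. The error is 1 − P(|Z1| < 1.96 and |Z2| < 1.96) for a bivariate normal with that ρ.
- The documents do not give p7 or q12. Assumed ranges: p7 from 0.30 to 0.65, q12 from 0.10 to 0.40.

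| p7 | q12 | ρ | Error, either measure |
|---|---|---|---|
| 0.30 | 0.10 | 0.22 | 9.6% |
| 0.40 | 0.20 | 0.41 | 9.3% |
| 0.49 | 0.20 | 0.49 | 9.1% |
| 0.65 | 0.30 | 0.89 | 7.1% |

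**3. Adding a log-rank test of recovery time.**
- If independent: 1 − 0.95³ = 14.3%, an upper reference only.
- Allowing for correlation by simulation under no effect: 40,000 trials per scenario, 150 and 200 per arm, 18 recovery patterns over the ranges above, follow-up to day 14.
- The log-rank statistic correlated 0.62–0.90 with the day-7 test and 0.76–0.94 with the day-12 test.
- Each test alone rejected at about 5%. At least one of the three rejected in 8.3–11.7% of trials, and in 10.8% at p7 = 0.49, q12 = 0.20.

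**4. Error if all had to succeed.** It cannot exceed that of any single test, so it is at most 5%.

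**5. Cost of splitting alpha over the two measures (0.025 each, z = 2.241).**
- N = ½ × [(2.241 + 0.842) / 0.1810]² = 145.03, rounded up to 146 per group.
- Power for each measure, if 0.40 versus 0.58 applies to it, is Φ(0.1810 × √(2n) − 2.241):

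| Evaluable per group | Origin | Power |
|---|---|---|
| 200 | planned, no loss | 91.6% |
| 160 | 200 less 20% | 84.1% |
| 120 | 150 less 20%, if 150 is per group | 71.3% |

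**The case against.** The best defence is that there is really one primary outcome. The summary says so, the lead line of Primary Outcome Measure says so, and both numbered items ask how many days, not what proportion. The day-7 and day-12 binary endpoints have to be read out of the time frames together with the logistic regression sentence. The log-rank sentence names no endpoint and follows text on severity conversion and PCR persistence, which are secondary, so counting it as a third primary test is an inference. The Data analysis section also gives no significance threshold; 5% comes from the sample-size alpha, and the 95% CI is consistent with it.

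Most of this stands, and it limits the point. A reader might infer that the trial's false-positive rate is already nearly doubled, or that three primary tests are each declared at 5%. The documents support neither: they give no rule that any single success is enough, and they label no test as primary. A reader might also infer that the day-7 and day-12 cuts throw away information. That is not an error in itself, because the recovery times are also analysed by Kaplan-Meier.

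The defence does not remove the gap. If there is one outcome, the protocol should not number two measures, plan a separate odds ratio for each, and leave all P values unadjusted without saying which analysis decides.

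**Conclusion.** The point holds in conditional form. The protocol describes its primary outcome in two ways, plans several analyses of it, names none as decisive and excludes adjustment throughout, while sizing the trial for one comparison at 0.05. Whether the 5% is kept depends on an unstated success rule. If any one success at 0.05 suffices, the error is about 7–10% over the two measures and about 8–12% over all three analyses. If all must succeed, it is not inflated.

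These figures rest on three assumptions: a 5% level for each test, a log-rank test applied to recovery time, and the recovery rates in the ranges shown. Every scenario tried under the any-one-success rule was clearly above 5%.

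**What to change.** **Preferred.** Name one deciding primary analysis. Time from randomisation to recovery, by log-rank test with Cox hazard ratio and 95% CI at two-sided 0.05, fits the summary best and uses the daily observations that the case record form already collects to day 14. Then:
- make the day-7 and day-12 odds ratios secondary;
- limit the no-adjustment sentence to non-primary analyses;
- state the time horizon, since the listed time frames are 7 and 12 days and the form runs to day 14;
- state one definition of recovery, since complete freedom from symptoms under Primary Outcome Measure differs from the clinical improvement criteria under Operational definition;
- restate the sample-size basis, because 0.40 versus 0.58 is a binary comparison and no power for a log-rank test is given.

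This is a short amendment plus a new sample-size justification, so slightly more than a change of wording.

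**Alternative.** Keep both measures primary, test each at 0.025 (or use Hochberg), and make the survival analysis secondary. The cost is some power. The requirement of 146 evaluable per group is met by 200 per group even after 20% loss, but not by 150 per group after that loss. The 200 and 150 figures must therefore be reconciled before this route is chosen.

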So it have been planned to conduct an experimental clinical trial using combination of ivermectin and doxycycline for treatment of COVID 19 along with the other standard care. It would be a randomized double blind placebo controlled Trial. The study would be conducted on 200 confirmed cases of Covid- 19. Another 200 patients will receive placebo.

The primary outcome would be the Days required for the Clinical improvement of the patients from the day of randomization.

Data will be analyzed using SPSS 20. Unpaired t-test would be used for testing quantitative data and for testing qualitative data two sample z- test would be used. For the comparison between two groups Hazard ratio, Kaplan-Meire curve, binary logistic regression would be used to see the outcome. Result of the study and statistical analysis will be presented by tables, figures, graphs, diagrams, charts and photographs. All these will have own legends (i.e. title) and will be serially numbered. Discussion will be done on the basis of result obtained from the study and comparing with similar studies done at home and abroad. Summarization will be drawn after discussion. Conclusion will be drawn depending upon the results and discussion.

PART - D

INTRODUCTION

On 31 December 2019, the World Health Organization (WHO) was formally notified about a cluster of cases of pneumonia in Wuhan City¹. On 7 January the causative virus was isolated and its genome sequence was shared on 12 January. The cause of the severe acute respiratory syndrome that became known as COVID-19 was a novel corona virus, SARS-CoV-2². The virus Spread quickly through out the universe in quick succession. The World Health Organization (WHO) on March 11, 2020, has declared the novel Corona virus (COVID-19) outbreak a global pandemic³.

Phylogenetic analysis suggests that SARS-CoV-2 originated in animals, probably bats, and was transmitted to other animals before crossing into humans at the Huanan wet market in Wuhan City⁴⁻⁵. It was the year 1918, when a new flu pandemic launched worldwide The pandemic infected 3% to 5% percent of the world's population including remote Pacific islands and the Arctic. The Life expectancy dropped by about 12 years⁶. The fatal casualties of the diseased had reached the number of the fifty million victims⁷.

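### Two numbered primary measures and a time-to-recovery comparison, all unadjusted and with none named as decisive, do not hold the planned two-sided 5% for the primary claim

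*Protocol*

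**What the plan says.** The project summary before Part D names a single primary outcome, days from randomisation to clinical improvement. The line under Primary Outcome Measure in section 4 (Methodology) repeats it. Two numbered items follow: "1. Early Clinical improvement of the patients", with a 7-day time frame, and "2. Late clinical recovery", with a 12-day time frame.

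The Data analysis paragraph gives both items their own effect measure: "Odds ratio will be formulated from linear logistic regression for early and late clinical recovery". It also assigns a Kaplan-Meier analysis to the duration of recovery, and compares the arms by log-rank test, hazard ratio and 95% CI without saying for which endpoint. On multiplicity it says "All P values will be two-sided and will be shown without" and continues "adjustment for multiple testing. All analyses will be performed according to the intention to treat principle".

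The sample size under Estimated enrollment ("All parameters were assumed as follows") uses one alpha of 0.05, beta of 0.20 and one binary response, 0.40 against 0.58. No time point is attached to that response.

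**The concern.** A plan that spends 5% once needs one result that decides. Here the same recovery data can be read at day 7, at day 12 and over the whole follow-up, each at an unadjusted 5%. The protocol gives no hierarchy, no requirement that all be significant and no designated test. The sample size does not settle it either, because its response rate could be the early measure, the late one or something else.

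If the result is significant at day 7 and not at day 12, or the reverse, the plan does not say whether the trial has met its primary aim. That choice would then be made with the data in view. The protocol calls this a phase III trial, so the error rate of the primary claim matters.

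**Working it through.** **1. The plan's own figure.** Inputs from Estimated enrollment: 0.40, 0.58, normal deviates 1.96 and 0.845.

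arcsin√0.40 = 0.6847 and arcsin√0.58 = 0.8657, so the difference is 0.1810.
N = ½ × (2.805 / 0.1810)² = 120.05, rounded up to 121 per group. The stated 121 is reproduced. It is the size for one test of one proportion at two-sided 5%.

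**2. Ceilings if the tests were independent.** Two tests: 1 − 0.95² = 9.75%. Three tests: 1 − 0.95³ = 14.3%. The actual tests share patients and are correlated, so the true figures are lower.

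**3. Error allowing for correlation.** No-effect trials were simulated with daily recovery times, 8,000 to 20,000 per scenario. The log-rank test ran to day 12 or 14, with a test of recovery by day 7 and another by day 12 (logistic Wald tests, or score tests in their place).

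Assumptions, none of them from the protocol: 20-58% recovered by day 7 and 40-90% by day 12, including exponential and Weibull (shape 1.5) curves, with 121 or 200 per arm. Each test alone rejected in about 4.3-5.5% of trials, as it should.

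Examples at 200 per arm:

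| Recovered by day 7 / day 12 | Log-rank cut | Day-7 or day-12 test | Any of three | Any of three, favouring drug |
|---|---|---|---|---|
| 20% / 40% | day 12 | 8.7% | 9.1% | 4.5% |
| 49% / 65% | day 12 | 8.8% | 9.3% | 4.7% |
| 40% / 80% | day 14 | 9.2% | 10.6% | 5.1% |
| 30% / 80% | day 14 | 9.5% | 11.3% | 5.6% |

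Over all scenarios:
- The two odds ratios alone: 8.1-9.5%.
- Any of the three: 8.8-11.3%.
- False benefit, any of the three: about 4.5-5.6%, against a nominal 2.5%.
- Any of the three, with late recovery read as recovery on days 8-12: about 11-12%.

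**4. Cross-check.** A multivariate normal calculation with correlations from the simulations (log-rank with day 7, log-rank with day 12, day 7 with day 12):
- 0.81, 0.96, 0.66: 8.5% for two tests, 9.0% for three.
- 0.73, 0.89, 0.41: 9.3% and 10.3%.
- 0.71, 0.78, 0.28: 9.5% and 11.2%.

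**5. What adjustment would cost.** Same arcsine formula at 80% power: alpha 0.025 (two tests) needs 146 per group, and alpha 0.0167 (three tests) needs 160. Power is Φ(√(2n) × 0.1810 − z):

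| Evaluable per group | 0.05 | 0.025 | 0.0167 |
|---|---|---|---|
| 200 | 95% | 92% | 89% |
| 160 (200 less 20%) | 90% | 84% | 80% |
| 120 (150 less 20%, if 150 is per group) | 80% | 71% | 66% |

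**The case against.** The strongest reply is that there is only one primary outcome. The summary and the line under Primary Outcome Measure both name days to clinical improvement, both numbered items ask how many days, and specific objective 2 is the duration needed for recovery. On that reading the odds ratios only describe a time-to-event result, and the inflation shrinks or disappears. The reading is tenable and it should shape the fix. It does not remove the problem, because the protocol still numbers two primary measures, gives each its own analysis and never calls any of them supportive. The summary itself lists a t-test, z-test, hazard ratio, Kaplan-Meier curve and logistic regression without saying which decides.

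Second, the log-rank sentence names no endpoint, and it comes after Cox models for severity conversion and persistent positivity, which are secondary. Linking it to recovery is a fair inference from the Kaplan-Meier sentence, not a statement in the text. Without that link the figure is about 8-9%.

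Third, a reader might infer that an early effect without a late one, or the reverse, gives contradictory primary answers. It does not: faster recovery by day 7 with no difference by day 12 is coherent. What is missing is a rule saying whether it counts as success. Nor is "Conclusion will be drawn depending upon the results and discussion" evidence of a plan to choose among results; it is report-outline wording.

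Fourth, ordering of tests is often left to a statistical analysis plan, which is not shown. But the protocol itself states non-adjustment for all P values, so a plan that adjusted the primary ones would contradict it.

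**Conclusion.** The point holds in conditional form. If any one of these analyses may support the primary claim, which the protocol does not exclude, the chance of a false significant primary result is about 8-9% for the two odds ratios and about 9-11% with the log-rank test. It reaches about 12% if late recovery means recovery on days 8-12. False claims of benefit roughly double, from 2.5% to about 4.5-5.6%.

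A reader might infer that the protocol lays down three primary tests and that its error is therefore a known 9-10%. The documents do not support that. They name one outcome in two places, leave the log-rank endpoint to inference and give no recovery-time distribution, so every figure here depends on assumed curves. The ranges also count results significant against the drug. The point concerns the primary family only, not the secondary outcomes.

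**What to change.** Under Primary Outcome Measure and Data analysis, name one confirmatory test at two-sided 5%, in line with the single outcome in the summary: the log-rank test, with hazard ratio, for days from randomisation to clinical improvement. State that the day-7 and day-12 odds ratios are supportive, reported with confidence intervals, and cannot establish benefit alone. Limit the non-adjustment sentence to non-primary P values. Under Estimated enrollment, state that the calculation is for a binary response and not for the log-rank test.

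If early and late must both stay primary, test them by a fixed sequence or by Holm. Then either make the log-rank result supportive or include it in the same procedure, so that it is not left as an uncontrolled third route.

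The preferred version costs a few sentences and the option of claiming success on whichever version is significant. Holm also costs some power. With 200 per group it stays at about 92% at 0.025 and 89% at 0.0167. With about 120 evaluable per group it falls below 80%. The second case matters because the protocol gives 200 per group in one line and then "So at least 150 patients will be allocated randomly and power of this study will be 80"%, without saying whether the 150 is per group.
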